13.0 Provisions to Monitor the Data to Ensure the Safety of Subjects

13.1 Data will be monitored internally by the research manager. Any considerable deviations or concerns are to be addressed with the research manager and the principal investigator.

Expected adverse events from each intervention (radiotherapy and LLIT) are listed in the research protocol and are to be managed accordingly. For all adverse events, sufficient information should be obtained by the investigator to determine the causality, (i.e., study

drug or other illness). The investigator is required to assess causality and indicate that assessment on the CRF. Follow-up of the adverse event, after the date of therapy discontinuation, is required if the adverse event or its sequelae persist. Follow-up is required until the event or its sequelae resolve or stabilize at a level acceptable to the investigator. Adverse events that continue, or emerge within 30 days, after the patient's discontinuation or completion of the study will be followed until the events resolve, are considered stable, or can be ascribed to causes other than study treatment.

All serious AE meeting criteria for reporting will be reported per the University of Pittsburgh Institutional Review Board's policies. In the event of such adverse event, the investigator must report the event(s) via phone within 24 hours and a written report filed within 24 hours to the Principal Investigator.

14.0 Statistical Considerations

14.1 Study Design/Endpoints

This is a phase I/II clinical trial aiming to assess the safety and efficacy of low level laser therapy (LLLT) in mitigating radiation-induced dermatitis in patients undergoing radiation therapy for head and neck squamous cell carcinoma (HNSCC). The primary endpoint is documented Grade 3 or higher Adverse Events as per CTCAE v4.0. The secondary objectives are the assessment of patient-reported quality of life data, pain parameters and dermatologic quality of life responses. The secondary endpoints are:

- Quality of life data measured using the University of Washington Quality of Life Questionnaire (UW-QOL)
- Pain parameters assessed using Brief Pain Inventory (BPI)
- Dermatologic quality of life responses measured using the Dermatology Life Quality Index (DLQI) aimed at the evaluation of the safety and clinical activity of tiragolumab in combination with atezolizumab, carboplatin, and pemetrexed in the 1st line treatment of non-squamous NSCLC patients with untreated brain metastases.

14.2. Statistical Analysis Plan

14.2.1 Analysis of the Primary Endpoint

The main goal of this study is to descriptively estimate grade 3 or higher adverse events as per CTCAE v4.0. The frequency and percentage will be calculated along with its exact 95% CI.

All patients who enroll in the study, and received at least 1 dose of the study treatment are evaluable for safety analysis. As per NCI

CTCAE Version 5, the term toxicity is defined as adverse events that are classified as either possibly, probably, or definitely related to study treatment. The maximum grade for each type of toxicity will be recorded for each patient, and frequency tables will be reviewed to determine toxicity patterns. The incidence of treatment-emergent AEs and SAEs will be summarized by system organ class and/or preferred term, severity, and relationship to study treatment determined.

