4.0 Study Endpoints

- 4.1 Primary Endpoint: The primary endpoint is to characterize the rate of any Grade 3 or higher Adverse Events as per CTCAE v4.0 (Common Terminology Criteria for Adverse Events).
- 4.2 Secondary Endpoints: Several patient reported QOL metrics will be collected as secondary endpoints.
 - quality of life data measured using the University of Washington Quality of Life Questionnaire (UW-QOL)
 - pain parameters assessed using Brief Pain Inventory (BPI)
 - dermatologic quality of life responses measured using the Dermatology Life Quality Index (DLQI)

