6.0 Procedures Involved

6.1 Screening / Pre-treatment:

- Medical history
- Physical examination, including Karnofsky Performance Status and vital signs.
- Signed informed consent
- Subject body weight and height
- Quality of Life Assessments (UW QoL, BPI, DLQI)

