6.2 Evaluation during Treatment

- Patients will be treated with the 69 diode LED cluster probe. The wavelength utilized are both 660 nm and 850 nm. The average power density is 100 mW/cm² and the spot size is 0.2 cm². Treatment time is 60 seconds to each site. There are a minimum of nine treatment sites: (1) left forehead, (2) right forehead, (3) left upper cheek/malar region, (4) right upper cheek/malar region, (5) right lower cheek / trigeminal nerve mandibular division distribution, (6) left lower cheek / trigeminal nerve mandibular division distribution, (7) submental region, (8) left neck, (9) right neck. Patients will be pretreated with a minimum of 3 sessions over 7 days before starting radiotherapy. Patients will receive LLLT at least twice the week prior to initiation of radiation and then at least three times per week during the course of radiation treatment.

- Adverse Event Assessment (Grading of skin toxicity and mucositis by patient)
- Completion of patient reported DLQI during treatment week 5 and at end of treatment

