10.0 Risks to Subjects

10.1 There are few risks associated with low-level laser therapy. This treatment is non-invasive and uses a cold laser output. Infrequently, eye damage has occurred with prolonged visual contact with the laser. Further, patients using concomitant supplemental niacin may experience, facial flushing.

10.2 Although no reported grade 3 or greater toxicities for LLLT have been published, patients will be closely monitored by a certified nurse prior to each delivery. Patients will be instructed to seek alternatives to niacin if taking this medication at the time of enrollment to the study. Additionally, eye protection is provided to all patients and staff present in the examination room during delivery of LLLT to prevent any eye damage. Significant mucositis from radiation is expected. Appropriate supportive care will be provided including analgesia, local therapies, and potentially low level laser therapy. Patients will be monitored weekly by the treating physicians to appropriately manage and record potential toxicities. Patients developing dermatologic adverse events will be monitored for the development of inflammatory or infectious sequelae. Supportive therapies other than the investigational intervention may include the following:

- Antibiotics: The benefit of routine antibiotics in uncomplicated (uninfected) rash is unclear. Some clinicians have used oral minocycline (Minocin), mupirocin (Bactroban), or topical clindamycin (Cleocin). Rash complicated by cellulitis should be treated with appropriate antibiotics based on clinical judgment or microbial sensitivity analysis.
- Antihistamines: Benadryl or Atarax may be helpful to control itching.
- Topical Steroids: The benefit of topical steroids is unclear.
- Retinoids: No data to support use. Use is not advised.

- Benzoyl peroxide: Should NOT be used--may aggravate rash.
- Makeup: Rash can be covered with makeup; this should not make it worse (use a dermatologist-approved cover-up, e.g., Dermablend, or any other type of foundation). Remove makeup with a skin-friendly liquid cleanser, e.g., Neutrogena, Dove, or Ivory
- Skin Cleansing Liqui-Gel.
- Moisturizers: Use emollients to prevent and alleviate the skin dryness, e.g., Neutrogena Norwegian Formula Hand Cream or Vaseline Intensive Care Advanced Healing Lotion.
- Sunlight: It is recommended that patients wear sunscreen and hats and limit sun exposure during treatment as sunlight can exacerbate any skin reactions that may occur.

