14.3. Sample Size/Accrual Rate

As stated in Section 14.2, the main goal of this descriptive study is not for hypothesis testing. We plan to accrue 75 patients. With this sample size, the exact 95% CI for the grade 3 AE has a maximum width of 24%. For example, if the observed rate is 15/75 (20%), then the 95% CI will be (12%, 31%). The following is a table for the CI.

Observed proportion of grade 3 AE	Exact 95% CI for the grade 3 AE rate
5/75 (7%)	(2%, 15%)
10/75 (13%)	(7%, 23%)
15/75 (20%)	(12%, 31%)
20/75 (27%)	(17%, 38%)
25/75 (33%)	(23%, 45%)
30/75 (40%)	(29%, 52%)

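### The primary Grade 3+ adverse event rate pools the laser-only lead-in with radiotherapy and has no graded baseline, so it cannot be attributed to the laser

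*Combined protocol and SAP*

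**What the plan says.** Section 2.1 makes the safety of LLLT an objective of this single-arm study, alongside efficacy. Section 4.1 defines the endpoint: "The primary endpoint is to characterize the rate of any Grade 3 or higher Adverse Events as per CTCAE v4.0". Section 14.2.1 states the analysis: "The frequency and percentage will be calculated along with its exact 95% CI". The safety population is "All patients who enroll in the study, and received at least 1 dose of the study treatment are evaluable for safety analysis". The same section records the maximum grade per toxicity type and promises summaries of treatment-emergent events by term, severity and relationship to study treatment. It plans no analysis by period.

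Section 6.2 creates a laser-only period: "Patients will be pretreated with a minimum of 3 sessions over 7 days before starting radiotherapy". A later sentence in that section gives a different minimum for the same week, at least two sessions.

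Section 6.1 lists the screening assessments: medical history, height and weight, three questionnaires, and "Physical examination, including Karnofsky Performance Status and vital signs". No CTCAE, skin or mucosal grade is among them. Adverse event assessment first appears in section 6.2, without a frequency.

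On monitoring, section 10.2 says: "Although no reported grade 3 or greater toxicities for LLLT have been published, patients will be closely monitored by a certified nurse prior to each" laser session. It adds weekly recording of toxicity by physicians, with no stated start. Section 13.1 requires the investigator to record causality on the CRF.

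**The concern.** Once radiotherapy starts, severe events are expected whatever the laser does. Section 10.2 anticipates significant mucositis. Section 3.1 cites Grade 3 dermatitis of 18% with radiotherapy alone and 23% with cetuximab added. There is no control group against which to set this background.

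The design does contain a period in which laser exposure comes before radiation, and timing relative to the first fraction is an objective fact. The planned tables lose that information. A patient with Grade 3 events in both periods counts once in the primary rate. A skin reaction in the lead-in that is followed by worse radiation dermatitis appears only at the higher grade.

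Treatment-emergent status also needs a starting grade. The trial admits adjuvant as well as definitive patients, so some may enter with post-surgical or tumour-related conditions. Without a grade before the first session, a condition already present cannot be told reliably from a new one. A starting grade cannot be recovered dependably afterwards.

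**Working it through.** **Inputs.** N = 75 and an exact two-sided 95% CI (sections 14.3 and 14.2.1). Background Grade 3 dermatitis of 18% to 23% (section 3.1). The documents give no any-cause Grade 3+ background and no laser-specific rate, so the values used for these below are assumptions.

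**1. The plan's own figures.** The Clopper-Pearson limits are the beta quantiles B(0.025; x, n−x+1) and B(0.975; x+1, n−x). With n = 75, x = 15 gives 11.65% to 30.83%, which is the stated 12% to 31%. All six table rows reproduce. The widest interval is at x = 37 or 38: 37.6% to 61.1% for x = 37, a width of 23.6 points, which is the stated 24%. The precision statement is correct for the pooled rate.

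**2. What the pooled rate can show about the laser.** Assume laser events occur independently of a background rate b, with a true laser Grade 3+ rate e. Then the pooled rate = 1 − (1 − b)(1 − e).

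| b | e | Pooled rate | Count of 75 | Exact 95% CI |
|---|---|---|---|---|
| 23% | 0 | 23% | 17 | 14% to 34% |
| 23% | 5% | 1 − 0.77 × 0.95 = 26.9% | 20 | 17% to 38% |
| 60% (assumed) | 0 | 60% | 45 | 48% to 71% |
| 60% (assumed) | 5% | 1 − 0.40 × 0.95 = 62% | 46 | 49% to 72% |

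Within each pair the intervals overlap almost entirely. The 23% is a dermatitis-only figure from another trial, and the endpoint counts any event. The 60% row shows that a higher background hides a laser effect further.

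**3. What a lead-in table could show.** With no events among n patients, the upper limit is 1 − (α/2)^(1/n).
- 0/75, two-sided 95%: 1 − 0.025^(1/75) = 4.8%.
- 0/75, one-sided 95%: 1 − 0.05^(1/75) = 3.9%.
- 1/75: 0.03% to 7.2%. 2/75: 0.3% to 9.3%.
- Chance of at least one event, 1 − (1 − p)^75: 53%, 78%, 90% and 98% for assumed true lead-in rates p of 1%, 2%, 3% and 5%.

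These figures assume that all 75 patients complete the lead-in and are assessed in it.

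**4. Effect of a missing baseline.** A patient counted for a pre-existing Grade 3 condition who has no new Grade 3+ event adds 1/75 = 1.3 points to the rate. The documents do not say how many such patients to expect, so no total can be given.

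**5. Does causality assessment fill the gap?** Section 14.2.1 defines toxicity as events possibly, probably or definitely related to study treatment, but does not say whether that term means the laser alone or the laser with radiotherapy. Section 13.1 calls both radiotherapy and the laser interventions, yet the causes it names are study drug or other illness. An event due to radiotherapy or chemotherapy has no clear place in that scheme.

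**The case against.** The strongest reply is that the plan does not rely on the pooled rate alone. Causality goes on the CRF for every event, and events are summarized by relationship to study treatment. Section 14.3 also says that "the main goal of this descriptive study is not for hypothesis testing", and the declared descriptive precision is met. This stands. A reader might infer that the laser's safety can be seen only in the lead-in, or that the safety objective cannot be answered. The documents support neither: attributed tables will give some evidence, although it will be subjective and come from an unblinded single arm.

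It is also fair to say that the lead-in cannot carry the objective. It covers a minimum of two or three sessions, against at least three per week during radiation. The documents give no radiotherapy duration; if it were 6 to 7 weeks, that would be at least 18 to 21 sessions. The lead-in cannot show cumulative effects or effects on irradiated skin. Its events may come from the tumour or from surgery, so they too need a causality judgement. This also stands, and it makes the lead-in table a supplement.

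Finally, some baseline information exists: the history, examination, questionnaires and the nurse check before the first session. Eligibility excludes prior head and neck radiotherapy and concurrent serious infection, and requires a Karnofsky score above 70. These limit the problem. None of them, as written, yields a CTCAE grade against which to judge an event as new or worse.

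**Conclusion.** The point holds in a limited form. The primary Grade 3+ rate cannot be attributed to the laser, and treatment-emergent status has no graded baseline. The planned attribution reduces the first problem but does not remove it, because study treatment is undefined and the named causes leave out radiotherapy and chemotherapy.

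On size, a true 5% laser rate would shift the pooled estimate by about 4 points at a 23% background and 2 points at an assumed 60%, within an interval some 20 points or more wide. A clear lead-in would bound early Grade 3+ events at 4.8%. The first result assumes independent laser and background events; the second assumes complete lead-in assessment of all 75 patients. The baseline gap has no estimable total.

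This does not invalidate the descriptive primary analysis. It is an inexpensive improvement that should be made before enrolment, because baseline grades cannot be rebuilt reliably later.

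**What to change.** 1. **Baseline grade.** In section 6.1, record CTCAE grades of skin, mucosa and existing symptoms at the screening examination. In section 14.2.1, define treatment-emergent as new or higher in grade than at screening, and report the Grade 3+ rate on that basis. Align section 4.1 with this.
2. **Lead-in table.** In section 14.2.1, add a supplementary table of new or worsened events by grade, from the first LLLT session to just before the first radiotherapy fraction, with exact 95% CIs. Record grades at the nurse checks that section 10.2 already requires before each session. State that the table covers early, short-exposure toxicity only and may include tumour or surgical events.
3. **Attribution.** Define study treatment, and record causality separately for laser, radiotherapy and systemic therapy.
4. **Lead-in definition.** Reconcile the two minimum session counts in section 6.2, so that exposure in the lead-in table is defined.

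The cost is one CRF page, recording of grades at checks already planned, and one extra table. No added visits or patients are needed. The downside is that the headline rate changes slightly when pre-existing conditions drop out.

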1.0 Study Summary

Study Title	Utilization of Low Level Laser Therapy (LLLT) for Radiation-Induced Dermatitis in Patients with Head and Neck Squamous Cell Carcinoma (HNSCC)
Study Design	Single-arm, Phase I/II
Primary Objective/Endpoint	
Assess the safety and efficacy of low level laser therapy (LLLT) in mitigating radiation-induced dermatitis in patients undergoing radiation therapy for head and neck squamous cell carcinoma (HNSCC)
 
Endpoint: Documented Grade 3 or higher Adverse Events as per CTCAE v4.0

Secondary Objective(s)/Endpoints	
assessment of patient-reported quality of life data, pain parameters and dermatologic quality of life responses
 
Endpoints:
 
 • quality of life data measured using the University of Washington Quality of Life Questionnaire (UW-QOL) • pain parameters assessed using Brief Pain Inventory (BPI) • dermatologic quality of life responses measured using the Dermatology Life Quality Index (DLQI)
Research Intervention(s)/Investigational Agent(s)	THOR Laser system
IND/IDE #	N/A
Study Population	patients with histologically proven squamous cell carcinoma of the oral cavity, oropharynx, hypopharynx or larynx who are candidates for either definitive or adjuvant therapy consisting of a chemotherapy regimen and concurrent radiation therap
Sample Size	75 planned
Study Duration for individual participants	15 months

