2.0 Objectives

- 2.1 The study aims to assess the safety and efficacy of the utilization of low level laser therapy to mitigate radiation-induced dermatitis in patients undergoing definitive or adjuvant radiation therapy with head and neck squamous cell carcinoma.
- 2.2 The hypothesis is that low level laser therapy given prior to and during the course of treatment will decrease the rate of grade III dermatitis, a common finding seen in patients undergoing radiation therapy with head and neck squamous cell carcinoma. An additional goal of low level laser therapy is to increase wound healing.

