In this respect, cetuximab appears to have a different toxicity profile than that of traditional chemotherapy such as cisplatin. The most commonly reported side effect is the development of skin reactions including macular, papular, and pustular rashes, xerosis, fissures, telangiectasias, and hyperpigmentation of the hair and nails (Bernier et al., 2008). The most frequent of these reactions is an acne-like rash that predominately appears in areas rich in sebaceous glands. The acne-like rash comprises itchy erythematous follicular papules that evolve into pustules. Other presentations include diffuse erythema with follicular papulopustules and telangiectasia, a seborrhoeic dermatitis-like rash or, occasionally, an edematous facial erythema. In the absence of radiation, the acne-like rash can be seen within a few days of the initiation of treatment and peaks 2–3 weeks after starting therapy (Bernier et al., 2008).

The effect on the skin during the combination of cetuximab and radiation is of considerable interest, as it might require special care to reduce symptoms and severity. It appears that radiation may delay the onset of the cetuximab-induced rash as it typically appears within irradiated fields 3–5 weeks after initiation of treatment (Bernier et al., 2008). There appears to be no obvious relationship between the severity of cetuximab-associated acne-like rash outside irradiated fields and the severity of radiation dermatitis. The aforementioned Phase III trial (Bonner JA et al., 2010) revealed no statistically significantly increase in the incidence or severity of radiation dermatitis compared with radiotherapy alone. The incidence of grade 3 radiation dermatitis was 18% with RT alone and 23% with RT with cetuximab ($p = 0.27$). There was a slight increase in the median duration of radiation dermatitis in the cetuximab arm (11.1 weeks) compared with the RT-alone arm (9.4 weeks).

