12.0 Data Management

12.1 This prospective observational study seeks to describe the toxicities of patients undergoing this intervention. Rates of Grade 3 CTCAE toxicities will be documented, along with PR-QOL secondary endpoints, and will be compared to historical reports of toxicity in the literature.

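### The hypothesis concerns grade III dermatitis, but no planned estimate gives that rate, and the historical comparison in 12.1 states no attribution basis while 14.2.1 restricts 'toxicity' to events related to an undefined 'study treatment'

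*Combined protocol and SAP*

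**What the plan says.** - **Hypothesis (2.2).** LLLT before and during radiotherapy "will decrease the rate of grade III dermatitis".
- **Primary endpoint (4.1, 14.2.1).** The rate of any grade 3 or higher adverse event by CTCAE v4.0, reported as a frequency and percentage with an exact 95% CI. No attribution limit is stated.
- **Toxicity (14.2.1).** The same section then turns to another CTCAE version and narrows the term: "CTCAE Version 5, the term toxicity is defined as adverse events that are classified as either possibly, probably, or definitely related to study treatment". It continues: "The maximum grade for each type of toxicity will be recorded for each patient".
- **General adverse event summary (14.2.1).** Treatment-emergent events are "summarized by system organ class and/or preferred term, severity, and relationship to study treatment". This summary has no relatedness filter.
- **Historical comparison (12.1).** "Rates of Grade 3 CTCAE toxicities will be documented", and these "will be compared to historical reports of toxicity in the literature". It names no event type, comparator or attribution basis.
- **Historical dermatitis rates (3.1).** "The incidence of grade 3 radiation dermatitis was 18% with RT alone and 23% with RT with cetuximab". The text does not say whether these counts were filtered by attribution.
- **Study treatment.** No section defines it. The Study Summary lists one intervention, the "THOR Laser system". Section 13.1 calls both radiotherapy and LLLT interventions, yet frames causality as study drug against other illness. Section 11.1 describes the study treatment as acting against cancer.

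**The concern.** The trial has one arm, so the comparison in 12.1 is the only stated route from the data to the hypothesis in 2.2. That route needs a grade 3 dermatitis rate, and the plan does not commit to one. The primary rate mixes dermatitis with every other grade 3 or higher event. The one summary built on each patient's worst grade by event type applies to toxicity, and so carries the relatedness restriction.

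The restriction matters because radiation dermatitis is an expected effect of the background radiotherapy. An investigator who judges causality against the laser alone could reasonably rate it unrelated, the more so as 10.2 says that no grade 3 or greater toxicity of LLLT has been published. The filter would then remove the very events that LLLT is meant to prevent. If the historical rate counts all such events, the trial rate would look lower with no effect of LLLT. As the text does not settle the basis, it could be chosen after the results are known.

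**Working it through.** **1. The plan's own figures.** For x events in n = 75, the exact (Clopper-Pearson) 95% limits are the 0.025 quantile of Beta(x, n − x + 1) and the 0.975 quantile of Beta(x + 1, n − x). For x = 5, 10, 15, 20, 25 and 30 these give 2.2–14.9%, 6.6–23.2%, 11.7–30.8%, 17.1–38.1%, 22.9–45.2% and 28.9–52.0%. All six rows in 14.3 agree after rounding. The greatest width over all x is 23.55%, which the plan states as 24%. There is no arithmetic error, and nothing below changes these figures.

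**2. When a lean arises.** Three conditions must hold together:

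- 12.1 uses 'toxicities' in the restricted sense of 14.2.1;
- 'study treatment' means LLLT only;
- the historical rate counts events regardless of attribution.

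If study treatment includes radiotherapy, nearly all radiation dermatitis would count as related and the filter removes little. If 12.1 uses the word in its ordinary sense, there is no filter. If the historical rate is itself filtered, the mismatch shrinks.

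**3. Size if all three hold (illustration only).** Let p be the true all-cause grade 3 dermatitis rate, set equal to the historical rate so that LLLT has no effect. Let f be the share of events rated at least possibly related. The documents give no value for f, which can lie anywhere from 0 to 1. The values of p, 18% and 23%, come from 3.1 and serve only as examples, since 12.1 names no comparator.

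Expected count = 75 × p × f. Apparent rate = p × f. Shift = p × (1 − f). The exact CI is taken at the nearest whole count.

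| p | f (assumed) | Expected count | Apparent rate | Shift (points) | Nearest count, exact 95% CI |
|---|---|---|---|---|---|
| 18% | 1 | 13.5 | 18.0% | 0 | 14/75, 10.6–29.3% |
| 18% | 0.75 | 10.1 | 13.5% | 4.5 | 10/75, 6.6–23.2% |
| 18% | 0.5 | 6.8 | 9.0% | 9.0 | 7/75, 3.8–18.3% |
| 23% | 1 | 17.25 | 23.0% | 0 | 17/75, 13.8–33.8% |
| 23% | 0.75 | 12.9 | 17.25% | 5.75 | 13/75, 9.6–27.8% |
| 23% | 0.5 | 8.6 | 11.5% | 11.5 | 9/75, 5.6–21.6% |

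Over the full range of f, the shift runs from 0 to 18 points (p = 18%) or 0 to 23 points (p = 23%). For scale, the two historical arms differ by 23 − 18 = 5 points.

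**4. The reverse mismatch.** If the trial figure is all-cause and the historical one is filtered, the same shift p × (1 − f) works against LLLT. Both sides need the same basis.

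**The case against.** The strongest case is that the text leans toward the harmless reading. Section 12.1 pairs grade 3 toxicities with the patient-reported secondary endpoints, just as section 4 pairs the primary with the secondary endpoints, so 'toxicities' there may simply mean the unfiltered primary endpoint. Sections 6.2 and 10.2 also use the word in its ordinary sense, and 12.1 does not refer to the definition in 14.2.1. Section 13.1 calls radiotherapy an intervention. It also requires a causality assessment for all adverse events, so unrelated events are recorded, and 6.3 collects observer-reported skin reactions without reference to attribution. An all-cause dermatitis rate can therefore be recovered from patient-level data. Finally, 14.3 says the study is not for hypothesis testing, and the 18% rate for radiotherapy alone is a doubtful match for the chemoradiotherapy population in the Study Summary.

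Most of this stands, and it makes the lean a conditional risk. It does not close the gap. That a rate can be recovered does not make it a planned estimate: the general summary is by system organ class and/or preferred term, so a dermatitis line is not assured, and nothing ties 12.1 to it. A descriptive comparison still needs the same kind of count on both sides.

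A reader might infer that the primary rate itself is filtered by attribution. It is not: 4.1 covers any grade 3 or higher event, and the estimate in 14.2.1 carries no such limit.

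**Conclusion.** The point holds as a minor gap in definition and reporting. It is certain that no planned estimate gives the grade 3 dermatitis rate named in the hypothesis, that 'study treatment' is undefined, that 12.1 states no attribution basis, and that 14.2.1 refers to two CTCAE versions.

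A reader might go further and conclude that the planned comparison is biased toward benefit. The documents do not support that. The lean needs all three conditions in the working, and the wording elsewhere makes the first two doubtful. The third cannot be checked, because the attribution basis of the 18% and 23% is not given. Nor can the size be determined: the halving of 18% to 9% rests wholly on an assumed share of 50%. With no decision rule in the plan, no stated conclusion would change. The primary rate, N = 75 and the table in 14.3 stand.

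**What to change.** 1. In 14.2.1, add the proportion of evaluable patients whose worst radiation dermatitis is grade 3 or higher, regardless of attribution, with an exact 95% CI.
2. In 12.1, name this as the dermatitis figure to be compared with history. Use historical rates on the same attribution basis or, where the source's basis differs or is unknown, say so beside the comparison. An all-cause figure should not be set without comment against a rate whose basis is not known.
3. Define 'study treatment' for causality assessment, stating whether it includes radiotherapy, and bring 11.1, 13.1 and 14.2.1 into line with that definition.
4. Use one CTCAE version throughout: v4.0, as in the endpoint.
5. Optionally, report grade 3 or higher events at least possibly related to LLLT as a separate safety rate.

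The cost is one or two table lines and some wording. The dermatitis line needs no causality data. Only the optional LLLT-related rate depends on how the CRF records causality, and the CRF is not in the documents. The sample size and the interval table do not change.
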